8.4	EXPEDITED REPORTING OF ADVERSE EVENTS	65
8.5	STATEMENT OF CONFIDENTIALITY AND SUBJECT PRIVACY.....	66
8.5.1	Collection, storage and future use of biological samples and corresponding data	66
8.6	TRIAL MILESTONES	66
8.7	ADMINISTRATIVE STRUCTURE OF THE TRIAL	67
9.	REFERENCES	69
9.1	PUBLISHED REFERENCES.....	69
10.	APPENDICES	71
11.	DESCRIPTION OF GLOBAL AMENDMENTS.....	73
11.1	GLOBAL AMENDMENT 1	73
11.2	GLOBAL AMENDMENT 2	74
11.3	GLOBAL AMENDMENT 3	75

ABBREVIATIONS AND DEFINITIONS

ADME	Absorption, distribution, metabolism, and excretion
AE	Adverse event
AESI	Adverse events of special interest
$Ae_{faeces, 0-tz}$	Amount of analyte eliminated in faeces from the time interval from time 0 to the last quantifiable time point
$Ae_{faeces, t1-t2}$	Amount of analyte that is eliminated in faeces from the time interval t_1 to t_2
$Ae_{urine, 0-tz}$	Amount of analyte that is eliminated in urine from the time interval from time 0 to the last quantifiable time point
$Ae_{urine, t1-t2}$	Amount of analyte that is eliminated in urine from the time interval t_1 to t_2
ALCOA	Attributable, legible, contemporaneous, original, accurate
ALT	Alanine aminotransferase
AMS	Accelerator mass spectroscopy
AST	Aspartate aminotransferase
$AUC_{0-\infty}$	Area under the concentration-time curve of the analyte in plasma over the time interval from 0 extrapolated to infinity
$\%AUC_{tz-\infty}$	Percentage of $AUC_{0-\infty}$ obtained by extrapolation
AUC_{t1-t2}	Area under the concentration-time curve of the analyte in plasma over the time interval t_1 to t_2
AUC_{0-tz}	Area under the concentration-time curve of the analyte in plasma over the time interval from 0 to the last quantifiable data point
$AUC_{0-\infty}$	area under the concentration-time curve of the analyte in plasma over the time interval from 0 extrapolated to infinity
BI	Boehringer Ingelheim
BMI	Body mass index (weight divided by height squared)
BP	Blood pressure
CA	Competent authority
CatC	Cathepsin C
CatG	Cathepsin G
CL/F	Apparent clearance of the analyte in plasma after extravascular administration
$CL_R, t1-t2$	Renal clearance of the analyte in plasma from the time point t_1 to t_2
C_{max}	Maximum measured concentration of the analyte in plasma
COVID-19	Corona virus disease 2019
CRF	Case Report Form, paper or electronic (sometimes referred to as 'eCRF')
CT Leader	Clinical Trial Leader
CT Manager	Clinical Trial Manager

Proprietary confidential information © 2023 Boehringer Ingelheim International GmbH or one or more of its affiliated companies

CTP	Clinical trial protocol
CTR	Clinical trial report
DDI	Drug-drug interaction
DILI	Drug induced liver injury
ECG	Electrocardiogram
eCRF	Electronic case report form
eDC	Electronic data capture
EDTA	Ethylenediaminetetraacetic acid
EoS	End of Study (synonym for End of Trial)
F	Absolute bioavailability factor
$fe_{faeces,t1-t2}$	Fraction of administered drug excreted unchanged in faeces over the time interval from t_1 to t_2
$fe_{faeces,0-tz}$	fraction of [^{14}C]-radioactivity excreted in faeces expressed as percentage of the administered dose over the time interval from 0 to the last quantifiable time point
$fe_{urine,t1-t2}$	Fraction of administered drug excreted unchanged in urine over the time interval from t_1 to t_2
$fe_{urine,0-tz}$	fraction of [^{14}C]-radioactivity excreted in urine expressed as percentage of the administered dose over the time interval from 0 to the last quantifiable time point
FU	Follow-up
GCP	Good Clinical Practice
gCV	Geometric coefficient of variation
gMean	Geometric mean
IB	Investigator's brochure
IEC	Independent Ethics Committee
IPD	Important protocol deviation
IRB	Institutional Review Board
ISF	Investigator site file
λ_z	Terminal rate constant of the analyte in plasma
LC-MS/MS	Liquid chromatography with tandem mass spectrometry
LLOQ	Lower limit of quantification
MBq	Megabecquerel
MDA	Methylenedioxymethamphetamine
MDMA	Methylenedioxymethamphetamine
MedDRA	Medical Dictionary for Regulatory Activities
MRD	Multiple-rising dose
MRT_{ex}	Mean residence time of the analyte in the body, extravascular
mSv	Millisievert

Proprietary confidential information © 2023 Boehringer Ingelheim International GmbH or one or more of its affiliated companies

NE	Neutrophil elastase
NOAEL	no observed adverse effect level
NSP	Neutrophil serine protease
PK	Pharmacokinetic(s)
PKS	Pharmacokinetic set
PLS	Papillon-Lefèvre-Syndrome
PR	Pulse rate
PR3	Proteinase 3
QT interval	ECG interval from the start of the QRS complex to the end of the T wave
QTc interval	QT interval corrected for heart rate, e.g. using the method of Fridericia (QTcF) or Bazett (QTcB)
REP	Residual effect period
SAE	Serious adverse event
SCR	Screening
SOP	Standard operating procedure
SRD	Single-rising dose
ss	(at) steady state
$t_{1/2}$	Terminal half-life of the analyte in plasma
t_{\max}	Time from (last) dosing to the maximum measured concentration of the analyte in plasma
TS	Treated set
t_z	Time of last measurable concentration of the analyte in plasma
TSAP	Trial statistical analysis plan
ULN	Upper limit of normal
V_z/F	Apparent volume of distribution during the terminal phase after extravascular administration
WOCBP	Women of childbearing potential
XTC	Ecstasy

1. INTRODUCTION

BI 1291583 is an inhibitor of cathepsin C (CatC) and is being developed for the treatment of bronchiectasis.

1.1 MEDICAL BACKGROUND

Bronchiectasis is a heterogenous respiratory syndrome characterised by abnormal and irreversible dilated bronchi. Patients with bronchiectasis can have a variety of symptoms which include persistent cough, production of large volumes of sputum, dyspnea, chronic fatigue and hemoptysis. These symptoms are burdensome and are often associated with social stigmatism, urine incontinence, anxiety, depression and a reduced quality of life.

Underlying etiologies range from well characterised genetic diseases such as Cystic Fibrosis (CF) and Primary Ciliary Dyskinesia (PCD), asthma, Chronic Obstructive Pulmonary Disease (COPD), post infectious sequelae, and various autoimmune diseases such as inflammatory bowel disease or rheumatoid arthritis. However, the largest single underlying etiology is not yet determined, or idiopathic, bronchiectasis. The incidence of bronchiectasis is increasing worldwide. Previously classified as a rare or orphan disease, bronchiectasis not related to cystic fibrosis is estimated at 53 to 566 cases per 100 000 inhabitants. Prevalence increases with age and female gender [[R21-3309](#); [R21-3311](#)].

Bronchiectasis is characterised by neutrophilic bronchial inflammation. Serine proteases released by neutrophils (NSP), such as neutrophil elastase (NE), cause structural damage to the airways, mucus gland hyperplasia, impaired mucus clearance, and result in a vicious cycle of recurrent severe infections and further airway damage [[P13-15562](#)]. Free airway NE is particularly high in patients with bronchiectasis [[R18-3357](#)]. Damaged and dilated airways filled with mucus are an ideal growth medium, leading to chronic colonization with pathogens such as *Pseudomonas aeruginosa* (P. aeruginosa).

Irreversibly dilated airways, mucus gland hyperplasia, and impaired mucus clearance leads to recurrent acute severe pulmonary infections, referred to as an exacerbation. Exacerbations are a hallmark of bronchiectasis, leading to further airway damage and increased mortality.

Even though airway dilation is irreversible, the consequences might be mitigated.

There is no registered therapy that ameliorates the neutrophilic inflammation and tissue destruction mediated by uncontrolled NSP activity in the airways.

The current key pharmacological management option is as-needed antibiotics to treat pulmonary exacerbations. Bronchodilators and/or inhaled corticosteroids are used 'off-label' and dependent on underlying etiology with limited supportive evidence. Chronic antibiotic treatment, mucoactive therapies and physiotherapy (airway clearance) are also used.

Consequently, the medical need for an efficacious anti-inflammatory treatment for bronchiectasis is high.

By suppressing key effectors of airway inflammation and tissue destruction, inhibiting Cathepsin C (CatC) is expected to have anti-inflammatory and tissue-preserving effects, as well as to reduce mucus hypersecretion and to restore effective clearance of pathogenic

Proprietary confidential information © 2023 Boehringer Ingelheim International GmbH or one or more of its affiliated companies

bacteria. CatC inhibition is expected to reduce the rate and severity of pulmonary exacerbations of bronchiectasis and hence reduce hospitalisations, improve symptoms of cough and sputum, and improve health-related quality of life.

[figure not shown]
1.2 DRUG PROFILE

1.2.1 BI 1291583

[figure not shown]
1.2.1.1 Mechanism of action

CatC is a cysteine protease which is exclusively responsible for the activation of all NSP (neutrophil elastase, Cathepsin G, Proteinase 3) during myelopoiesis of neutrophils in the bone marrow [[R17-2915](#)].

[figure not shown]
BI 1291583 is a potent, selective, and reversible CatC inhibitor. CatC inhibition leads to suppression of the three key NSPs, neutrophil elastase (NE), proteinase 3 (PR3), and Cathepsin G (CatG). All three NSPs contribute to inflammation and tissue destruction. Neutrophil elastase impairs ciliary function and promotes mucus secretion, it cleaves CXCR1, CD14, CD16 on neutrophils and thus disables bacterial killing and impairs innate immunity. By crippling normal host opsonophagocytosis, bacterial persistence is promoted. Epithelial cells, induced by NE, release IL-8, which in turn recruits even more neutrophils that are unable to kill bacteria, i.e. excessive amounts of NE induce ineffective antibacterial defense [[R18-3384](#)]. Inhibition of CatC is expected to lead to neutrophils with a decreased loading of active NE, PR3, and CatG, resulting in an improvement of the protease-antiprotease balance in the lungs of patients with bronchiectasis.

[figure not shown]
Proprietary confidential information © 2023 Boehringer Ingelheim International GmbH or one or more of its affiliated companies

[figure not shown]
Proprietary confidential information © 2023 Boehringer Ingelheim International GmbH or one or more of its affiliated companies

[figure not shown]
Proprietary confidential information © 2023 Boehringer Ingelheim International GmbH or one or more of its affiliated companies

[figure not shown]
Proprietary confidential information © 2023 Boehringer Ingelheim International GmbH or one or more of its affiliated companies

[figure not shown]
Proprietary confidential information © 2023 Boehringer Ingelheim International GmbH or one or more of its affiliated companies

Proprietary confidential information © 2023 Boehringer Ingelheim International GmbH or one or more of its affiliated companies

Proprietary confidential information © 2023 Boehringer Ingelheim International GmbH or one or more of its affiliated companies

1.3 RATIONALE FOR PERFORMING THE TRIAL

The trial is intended to investigate the basic pharmacokinetics, excretion pathways and metabolism of BI 1291583.

The investigation of these processes, including the quantitative assessment of elimination pathways and drug metabolites, is necessary for an in-depth understanding of the pharmacokinetics of BI 1291583. In addition, the data are required for future submission to regulatory authorities.

1.3.1 Nomenclature

In this clinical trial protocol the following nomenclature applies:

- [¹⁴C]-radioactivity: Radioactivity measured by [¹⁴C]
- [C-14] BI 1291583: BI 1291583 labelled with ¹⁴C, “hot” drug substance
- BI 1291583: non-labelled, “cold” drug substance
- BI 1291583 (C-14): Drug product, mixture of “hot” and “cold” drug substance, 1:50

1.4 BENEFIT - RISK ASSESSMENT

1.4.1 Benefits

Participation in this clinical trial is without any (therapeutic) benefit for healthy subjects. Their participation, however, is of major importance for the development of BI 1291583.

Proprietary confidential information © 2023 Boehringer Ingelheim International GmbH or one or more of its affiliated companies

1.4.2 Risks

Subjects are exposed to risks of trial procedures and risks related to the exposure to the trial medication. An overview of trial-related risks is given in Table [1.4.2: 1](#).

Table 1.4.2: 1 Overview of trial-related risks for this trial

Possible or known risks of clinical relevance for this trial	Summary of data, rationale for the risk	Mitigation strategy
Investigational Medicinal Product: BI 1291583		
Possible effects of CatC inhibition	Based on observations in patients with the rare genetic disease Papillon-Lefèvre Syndrome (PLS), clinical signs and symptoms of life-long complete absence of CatC are palmoplantar hyperkeratosis, severe periodontitis, alveolar bone resorption, loss of deciduous and permanent teeth, and an increased susceptibility to infections [R17-3100] . The immune-deficiency in PLS patients is generally mild [R17-3101] .	
- Such effects are not expected to occur after a single dose.- Exclusion of subjects with relevant immunodeficiency or receiving immunosuppressive medication or having an acute infection.- Regular clinical and laboratory monitoring for infection.- - - - -
Redacted content		

Proprietary confidential information © 2023 Boehringer Ingelheim International GmbH or one or more of its affiliated companies

Table 1.4.2: 1: Overview of trial related risks and mitigation strategy (cont.)

Possible or known risks of clinical relevance for this trial	Summary of data, rationale for the risk	Mitigation strategy
Drug-induced liver injury (DILI)	Rare but severe event, thus under constant surveillance by sponsors and regulators. Although not specifically expected with this molecule or mechanism, monitoring for DILI is standard in drug development.	Timely detection, evaluation, and follow-up of laboratory alterations in selected liver laboratory parameters. (see Section 5.2.6.1.4)
Trial procedures		
Blood sampling	Blood sampling is a standard clinical procedure. As with all blood sampling, there is a risk of mild pain, local irritation, or bruising (a black or blue mark) at the puncture site. Furthermore, there is a small risk of light-headedness and/or fainting. In rare cases, the puncture site can also become infected or nerves may be damaged, inducing long-lasting abnormal sensations (paresthesia), impaired sensation of touch and persistent pain.	
 - Close clinical monitoring for AEs - Selection of experienced sites and site staff 
Blood sampling The total volume of blood to be withdrawn per subject during the entire trial was calculated as 464.2 mL, i.e. it will not exceed the volume of a normal blood donation (500 mL). No health-related risk to healthy subjects is expected from withdrawal of this volume of blood.

Table 1.4.2: 1: Overview of trial related risks and mitigation strategy (cont.)

[figure not shown]
Possible or known risks of clinical relevance for this trial	Summary of data, rationale for the risk	Mitigation strategy
Other risks		
Pandemic situations (i.e. SARS-CoV-2)	Travelling to site, being at site for assessments (standard risk in the current pandemic situation).	
 Travel is reduced to a minimum. Appropriate testing and infection control during the study. For possible additional modifications in pandemic situation see Flow Chart and site specific risk management procedures.
Risk related to the administration of BI 1291583 (C-14)	BI 1291583 (C-14) contains the isotope [¹⁴ C] which is necessary for the purposes of this mass balance trial. Therefore, subjects will be exposed to ionizing radiation. The effective whole body dose that each subject receives from one administration of \approx 0.36 MBq is approx. 0.04 mSv.	
The effective whole body dose in this study is 0.04 mSv. This is lower than the limit specified by:
 
International Commission on Radiological Protection (ICRP) Category 1, (<0.1 mSv – risk defined as trivial)
 
For details on the radiation burden calculation please refer to Appendix 10.1. For clinical investigations to study the disposition, metabolism and excretion of new pharmaceutical compounds in man an effective dose of up to 1.0 mSv is considered acceptable [R15-3219].

1.4.3 Risk related to the COVID-19-pandemic

The available evidence does not suggest an increased risk of acquiring an infection with a viral pathogen targeting the airways, including SARS-CoV-2, nor of a particularly more severe clinical presentation in case of such an infection, with suppression of CatC. Currently available evidence does also not suggest an increased risk of bacterial superinfection in case of COVID-19. CatC inhibition is not expected to reduce the efficacy of a COVID-19 vaccine to induce an immune response; and vice versa, vaccination is not expected to reduce the efficacy of the CatC inhibitor. Please also refer to the current Investigator's Brochure (IB) for BI 1291583 [[c18711868](#)].

1.4.4 Discussion

By reducing NE, PR3, and CatG activities BI 1291583 is expected to break the vicious cycle of bronchiectasis. BI 1291583 is expected to increase the time to pulmonary exacerbation, improve lung function and burdensome symptoms and, ultimately, quality of life.

Summary

The nature of the target and the mechanism of action of BI 1291583 is well understood.

In the current trial, healthy male volunteers will receive a single oral dose [REDACTED] BI 1291583 (C-14). Each participating subject will receive only one radioactive dose. The trial design is optimized to collect as much relevant information as possible on the pharmacokinetics of BI 1291583 without exposing participating volunteers to undue risk.

However, there is always the potential for subjects receiving medication to experience adverse events (AEs), and rarely also serious adverse events (SAEs).

The risk associated with the expected maximal radiation burden falls in ICRP category 1 with trivial level risk. This is considered to be acceptable.

Healthy subjects are not expected to have any direct benefit from participation in this trial. Considering the medical need of the development of an effective treatment to slow the progression of bronchiectasis for patients with this disease, the Sponsor considers that the benefit outweighs the potential risks and justifies exposure of healthy human volunteers. The

Proprietary confidential information © 2023 Boehringer Ingelheim International GmbH or one or more of its affiliated companies

benefit/risk assessment for the administration of BI 1291583 to healthy subjects remains unaltered also in face of the COVID-19 pandemic.

2. TRIAL OBJECTIVES AND ENDPOINTS

2.1 MAIN OBJECTIVES, PRIMARY AND SECONDARY ENDPOINTS

2.1.1 Main objectives

The main objective of this trial is to

- assess the mass balance and total recovery of [¹⁴C]-radioactivity in urine and faeces following a single oral dose of [REDACTED] BI 1291583 (C-14)
- provide plasma and urine samples for pharmacokinetic investigations
- provide plasma, urine, and faeces samples for metabolic profiling and structural identification of metabolites

2.1.2 Primary endpoints

Primary endpoints will be the mass balance and total recovery of [¹⁴C]-radioactivity in urine and faeces:

[figure not shown]
- $fe_{urine, 0-tz}$ (fraction of [¹⁴C]-radioactivity excreted in urine expressed as percentage of the administered dose over the time interval from 0 to the last quantifiable time point)
- $fe_{faeces, 0-tz}$ (fraction of [¹⁴C]-radioactivity excreted in faeces expressed as percentage of the administered dose over the time interval from 0 to the last quantifiable time point)

Timeframe: The timeframe for determination of these endpoints depends on individual excretion/ recovery of radioactivity and may vary between 2 and 6 weeks, inclusive, after drug administration.

[figure not shown]
2.1.3 Secondary endpoints

The following secondary endpoints will be evaluated for [¹⁴C]-radioactivity, BI 1291583 and five metabolites (M407(1) / BI 1373234, M396(1) / CD 18507, M397(1) / CD 17849, M549(1) / CD 16785) and M141(1) / CD 16426 in plasma:

[figure not shown]
- C_{max} (maximum measured concentration of the analyte)
- AUC_{0-tz} (area under the concentration-time curve of the analyte over the time interval from 0 to the last quantifiable time point)

[figure not shown]
Proprietary confidential information © 2023 Boehringer Ingelheim International GmbH or one or more of its affiliated companies

Proprietary confidential information © 2023 Boehringer Ingelheim International GmbH or one or more of its affiliated companies

Proprietary confidential information © 2023 Boehringer Ingelheim International GmbH or one or more of its affiliated companies

2.2.2.2 Safety and tolerability

Safety and tolerability of BI 1291583 will be assessed based on:

- Adverse events (including clinically relevant findings from the physical examination)
- Safety laboratory tests
- 12-lead ECG
- Vital signs (blood pressure, pulse rate)

Proprietary confidential information © 2023 Boehringer Ingelheim International GmbH or one or more of its affiliated companies

3. DESCRIPTION OF DESIGN AND TRIAL POPULATION

3.1 OVERALL TRIAL DESIGN

The trial will be performed as an open-label, single-arm, single-dose trial in healthy male subjects to investigate the basic pharmacokinetics of BI 1291583, its metabolites (M407[1] / BI 1373234, M396(1) / CD 18507, M397(1) / CD 17849, M549(1) / CD 16785 and M141(1) / CD 16426) and [¹⁴C]-radioactivity, including mass balance, excretion pathways and metabolism following a single oral dose of [REDACTED] BI 1291583 (C-14).

A total of 8 healthy male subjects are planned to participate in the trial.

The planned radioactive dose per subject is approximately ≈ 0.36 MBq (0.04 mSv).

On Day 1, subjects will receive the drug product, i.e. [REDACTED] BI 1291583 (C-14) and will then stay in the study centre up to the morning of Day 15 for collection of samples of blood, urine and faeces, and if applicable for collection of vomit (within 24 hours after drug administration).

[REDACTED]

Subjects will be readmitted to the study centre for 24 h collection intervals of urine and faeces on Days 21, 28, 35, and 42, if release criteria have not been met before. Within 24 hours before each of these once-weekly in-house collection intervals, subjects are to collect faeces at home. This 24-h interval home collection faeces will be used for analysis in case no defecation occurs in the subsequent 24 h in-house collection interval. Otherwise it will be discarded.

For determination of whether release criteria have been reached for individual subjects, [¹⁴C]-radioactivity will be measured in excreta (urine, faeces), and vomit, if applicable. The actual recovery results will be reported as a percentage of the administered dose.

If the following release criteria have been met, the subsequent 24 h collection intervals after Day 15 will not be performed:

- Greater than or equal to 90% of the administered [¹⁴C] dose has been recovered in urine and faeces combined over the investigational period

and

- If <1% of the [¹⁴C] dose administered has been collected in urine and faeces within 2 separate, consecutive 24-h intervals

Note:

For calculation of release criteria during clinical conduct the fraction of administered [¹⁴C] dose will be rather underestimated as it will be based on the available samples, only. For the final analysis, the total excreted [¹⁴C]-radioactivity will be derived including an interpolation method to account for the time periods without samples taken (see Section [7.2.2](#)).

In this trial the term “release” does not mean that no further assessments are required and that the end of study examination can be performed. Subjects need to return for blood sampling

Proprietary confidential information © 2023 Boehringer Ingelheim International GmbH or one or more of its affiliated companies

(PK and metabolite profiling) even if formal release criteria for the excretion of ¹⁴C-labeled drug material in excreta have been met.

If a subject is unable to attend one of the ambulatory visits, they may be allowed to reschedule the visit if needed. Irrespective of whether release criteria have been met or not, no further collections are planned after collection interval day 42-43.

[figure not shown]
An overview of all relevant trial activities is provided in the [Flow Chart](#). For visit schedule and details of trial procedures at selected visits, refer to Sections [6.1](#) and [6.2](#), respectively.

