5.3.2.4 Collection of vomit

If vomiting occurs within 24 hours after drug administration the vomit will be collected to calculate the weight and determine the [¹⁴C]-radioactivity levels. For a description of vomit sample preparation, sample storage, labelling, and sample shipment refer to the laboratory manual.

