7.2.1.2 Pharmacokinetics

The pharmacokinetic parameters listed in Section [2.1](#) and [2.2.2](#) for drug BI 1291583 and its metabolites will be calculated according to the relevant BI internal procedures.

Plasma, urine, faeces, and vomit (as applicable) concentration data and parameters of a subject will be included in the statistical pharmacokinetic (PK) analyses if they are not flagged for exclusion due to a protocol deviation relevant to the evaluation of PK (to be decided no later than in the Report Planning Meeting) or due to PK non-evaluability (as revealed during data analysis, based on the criteria specified below). Exclusion of a subject's data will be documented in the CTR.

Important protocol deviations may be

- Incorrect trial medication taken, i.e. the subject received at least one dose of trial medication the subject was not assigned to
- Incorrect dose of trial medication taken
- Use of restricted medications

Plasma, urine and faeces concentrations and/or parameters of a subject will be considered as non-evaluable, if for example

- The subject experienced emesis that occurred at or before two times median t_{max} of the respective treatment (Median t_{max} is to be determined excluding the subjects experiencing emesis). For collection of vomit see Section [5.3.2.4](#).
- A pre-dose concentration (in plasma) is $>5\%$ C_{max} value of that subject
- Missing samples/concentration data at important phases of PK disposition curve

Plasma, urine, faeces, and vomit (if applicable) concentration data and parameters of a subject which are flagged for exclusion will be reported with its individual values but will not be included in the statistical analyses. Descriptive and inferential statistics of PK parameters will be based on the PKS.

[figure not shown]
Only concentration values within the validated concentration range and actual sampling times will be used for the calculation of pharmacokinetic parameters. Concentrations used in the pharmacokinetic calculations will be in the same format provided in the bioanalytical report, (that is, to the same number of decimal places provided in the bioanalytical report).

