## **7.4 PRIMARY OBJECTIVE ANALYSIS**

### **7.4.1 Main analysis**

The primary and secondary endpoints will be analysed descriptively, as described in the **CTP Section 7.2.2** and **Section 7.2.3**.

**CTP Section 7.2.2:** “*To avoid underestimation of the total recovery of [ $^{14}\text{C}$ ], the excretion during the non-sampling phase of the study will be estimated using linear interpolation between the observed 24-h sampling periods before and after the non-sampling period for urine and faeces respectively.*”

The analysis of primary and secondary endpoints will be based on the PKS. Subjects in the PKS may not contribute data to every statistical analysis of PK endpoints, in case specific PK endpoints of this subject are missing or excluded for the following reasons.

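### Does measuring vomit for the release decision conflict with a release sum that counts only urine and faeces?

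*Protocol*

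**What the plan says.** Protocol Section 3.1 introduces the measurement with its purpose, "For determination of whether release criteria have been reached for individual subjects", and then lists the material: "radioactivity will be measured in excreta (urine, faeces), and vomit, if applicable". Recovery is reported as a percentage of the administered dose.

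Two criteria follow, and both must be met before the collections after Day 15 are dropped. The first requires that at least 90% of the "dose has been recovered in urine and faeces combined over the investigational period". The second requires that less than 1% of the dose was collected in urine and faeces within two separate, consecutive 24-hour intervals. The flow chart repeats both. Section 3.1 adds that subjects return for blood sampling even after release, and that no collection takes place after Day 42-43, whether or not the criteria are met.

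Section 5.3.2.4 covers the sampling: "If vomiting occurs within 24 hours after drug administration the vomit will be collected to calculate the weight", and its radioactivity is determined. It does not say how the result enters recovery. Section 7.2.1.2 states that "Plasma, urine, faeces, and vomit (as applicable) concentration data and parameters of a subject will be included in the statistical pharmacokinetic (PK) analyses" provided they are not flagged for a relevant protocol deviation or "due to PK non-evaluability (as revealed during data analysis, based on the criteria specified below". One example given there of non-evaluability is emesis at or before twice the median tmax.

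On the endpoints, Section 2.1.2 says "Primary endpoints will be the mass balance and total recovery of" radioactivity in urine and faeces, and lists the urinary and faecal fractions. SAP Section 7.4.1 notes that "Subjects in the PKS may not contribute data to every statistical analysis of PK endpoints".

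**The concern.** Section 3.1 gives the vomit measurement a purpose that the criteria a few lines later do not use. A site or laboratory could take the first sentence to mean that vomited radioactivity counts as recovered, or that it should come off the dose. For a subject who vomits, these readings can lead to different release decisions. At stake are up to four further weekly 24-hour collections (from Days 21, 28, 35 and 42), and hence the window over which that subject's urinary and faecal fractions, the primary endpoints, are measured. The emesis rule in Section 7.2.1.2 does not settle the matter, because it is applied at analysis and needs the median tmax, whereas release is decided during conduct.

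A second question goes with it. Total recovery is named among the primary endpoints, but the visible text does not define it as a per-subject sum or say how a subject with one route excluded would enter it.

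**Working it through.** **Inputs.** From the protocol: the 90% threshold, the materials summed, the 24-hour vomit window and the end of collection at Day 42-43 (Sections 3.1 and 5.3.2.4), and the eight planned subjects (Section 7.5). The 90% is a fixed rule, so there is no derived figure to reproduce. The documents give neither an emesis rate nor a vomit share. Assumed, therefore: v, the percentage of dose in vomit, and r, the share of the remaining dose recovered in urine and faeces.

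**Step 1: what urine plus faeces must reach, in % of administered dose.** Reading A is the criterion as written: 90. Reading B adds vomit to the sum: 90 − v. Reading C takes vomit off the dose: 0.90 × (100 − v).

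| v | A | B | C |
|---|---|---|---|
| 0 | 90 | 90 | 90 |
| 5 | 90 | 85 | 85.5 |
| 10 | 90 | 80 | 81 |
| 20 | 90 (only 80 remains) | 70 | 72 |

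Without vomiting the three readings agree. With vomiting, A is always the strictest, so it can only delay release, never bring it forward.

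**Step 2: when A can be met.** r × (100 − v) ≥ 90 gives v ≤ 100 − 90/r:

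- r = 1.00: v ≤ 10.0
- r = 0.95: v ≤ 5.3
- r = 0.92: v ≤ 2.2

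Above 10% the first criterion cannot be met, and collection runs to Day 42-43. Under B, v + r × (100 − v) is at least 90 for any v once r ≥ 0.90.

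**Step 3: what a different decision is worth.** If a subject were released under B but not under A, the most that later collection could still have found is everything not yet recovered, (1 − r) × (100 − v).

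- v = 8, r = 0.95: A gives 0.95 × 92 = 87.4 (not met); B gives 87.4 + 8 = 95.4 (met). Remainder 0.05 × 92 = 4.6; on a mean of eight, 4.6/8 = 0.58.
- v = 5, r = 0.92: A gives 0.92 × 95 = 87.4 (not met); B gives 92.4 (met). Remainder 0.08 × 95 = 7.6; 7.6/8 = 0.95.

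With six evaluable subjects, the minimum in Section 7.5, these become 4.6/6 = 0.77 and 7.6/6 = 1.27. They are upper limits for both routes together, and they arise under the reading that is not written. Under A the later collections take place.

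**Step 4: the second criterion.** It is the same under all three readings, because it names urine and faeces only. A decision changes only for a subject who also meets it, that is, one whose excretion has already slowed.

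**Step 5: the passages side by side.** The first sentence says what is measured, and it lists vomit apart from excreta, which it glosses as urine and faeces. The criteria say what is summed. Section 3.1 later describes the release criteria as concerning labelled material in excreta. Sections 4.1.4, 5.3.2.3 and 6.2.2 all refer back to Section 3.1 for the criteria and add no vomit term. The SAP adds none either.

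**The case for a change.** The strongest case for a change is that a stated purpose should mean something. If vomit is measured in order to decide release, a reader may expect it to count, and two competent people could apply the rule differently. For a subject with more than 10% of the dose in vomit, the literal rule makes release impossible, which brings extra in-house stays and home collections.

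Part of this stands. The purpose clause is loosely worded, and the literal rule does put a burden on such a subject. But counting vomit would mean adding a term to a criterion that names its terms, identically in two places. The burden is bounded at four collections, and the subject returns for blood sampling regardless. The note in Section 3.1 already accepts that the release calculation runs low because it uses available samples only, so a rule that leans towards more collection fits the design.

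The emesis rule also limits the consequence, although it does not decide release. Where emesis occurs at or before twice the median tmax, that subject's urine and faeces parameters may be flagged. They would then be listed but kept out of the summaries, whichever way release was decided. How much of the 24 hours this covers cannot be judged without a median tmax.

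The question about total recovery is separate from vomit. Section 3.1 says total excreted radioactivity will be derived for the final analysis. Visible protocol numbering passes from 2.1.3 to 2.2.2.2, and the SAP contents list shows redacted entries after 5.2.2 and 7.4.1. A definition may stand there, so its absence cannot be held against the plan. Where every included subject has both fractions, the mean total equals the sum of the two route means. Any figure for the unequal case would need invented excretion values.

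**Conclusion.** This is a loosely worded purpose clause, and no change to the plan is needed. The release criteria are explicit about what is summed. Following them literally gives no wrong result: it can only keep a subject in collection longer, up to the fixed end at Day 42-43, and it leaves the definitions of the two primary fractions untouched. If vomit were counted instead, the excretion missed in the two examples would be at most about 0.6 and 0.95 percentage points on a mean of eight, for one affected subject who also meets the second criterion. This rests on assumed vomit shares of 8% and 5% and assumed recoveries of 95% and 92%. A larger remainder or several such subjects would raise it, but only under a reading the text does not state. In a descriptive trial without hypothesis tests, that does not alter any conclusion. The per-subject total is a possible missing definition that redacted text may supply, and it calls for no change either.
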